6.2.3 Long-term Follow-up

For both phase I and phase II, a long-term follow-up period will start after the EOCT, ED or EOAC visit and subjects will be followed up every 3 months (±2 weeks) until lost to follow-up, withdrawal of consent, death or a maximum of 5 years, whichever occurs first. During this period, if subjects do not receive any other chemotherapy or radiotherapy, they will be followed for the antitumour effect and long-term safety of the IMP. Otherwise, subjects will be followed for antitumour effect up to the administration of any other chemotherapy or radiotherapy and for the safety aspects (in particular for haematological and renal safety) for the remainder of the long-term follow-up period.

Five Years After the EOCT, ED or EOAC Visit

In the long-term follow-up period, subjects will be followed up every 3 months (± 2 weeks) until lost to follow-up, withdrawal of consent, death or a maximum of 5 years, whichever occurs first. The following safety assessments will be performed by the site: these assessments can be performed on-site or by remote visit:

- Survival status
- Haematology and biochemistry tests (haemoglobin, platelet count, white blood cell count (absolute counts), AST, ALT, total bilirubin (with conjugated bilirubin if total bilirubin is abnormal i.e. outside the laboratory normal range), creatinine and urea) performed until the start of new antitumour treatment or up to 2 years after the EOCT, ED or EOAC visit, whichever comes first. Laboratory tests can be performed locally; results should be collected from the local laboratory.
- All AEs and serious adverse events (SAEs) are to be reported up to 6 months after the EOCT, ED or EOAC visit or until new antitumour treatment starts, whichever comes first. Thereafter, only AEs and SAEs related to the IMP or study procedure should be reported for the remainder of the safety follow-up period.
- Subsequent antitumour treatment

All collected data will be recorded in the eCRF.

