8.1.2.3 Reporting of Adverse Events

Any AEs/SAEs, irrespective of causality, are to be reported to the sponsor up to 6 months after the EOCT, ED or EOAC visit or until new antitumour treatment starts, whichever comes first. After this timepoint, up to the end of the 5-year follow-up period, AEs/SAEs should only be reported if the event is evaluated as related to the IMP or study procedure by the investigator.

Any AE considered related to IMP administration that the investigator becomes aware of after completion of the EOS/ED visit must be reported to the sponsor and will be recorded in the eCRF. EOS for AE reporting is defined as the end of the 5-year follow-up or death.

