8.1.7 Deaths

All AEs resulting in death during the study period must be reported as SAEs.

The convention for recording deaths is as follows:

- adverse event term: lead cause of death (e.g. multiple organ failure, pneumonia, myocardial infarction);
- outcome: fatal.

The only exception is if the cause of death is unknown (i.e. sudden or unexplained death), in which case the AE term may be reported as "death" or "sudden death".

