### 1.3.2 Subjects assessments

#### 1.3.2.1 Safety assessments

- Adverse events (AEs) monitored from the time that the subject gives informed consent and throughout the study, elicited by direct, nonleading questioning or by spontaneous reports. All AEs, irrespective of causality, should be reported to the sponsor up to 6 month after the EOCT, ED and EOAC visit or until new antitumour treatment starts, whichever comes first. AEs reported after this timepoint up to the end of the 5-year follow-up should only be reported if evaluated as related to the IMP or study procedure by the investigator;
- Clinical safety assessments:
  - Physical examination assessed at screening, at Day 1 pre-dose (and up to 24 hours (replaced by up to 48 hours from protocol V7.0) before IMP infusion for cycle 1 only), Day 15 and Day 29 of both cycles 1 and 2, at EOCT/ED visit, at Day 1 and Day 29 of each additional cycle (if applicable), at EOAC/ED visit (if applicable) and every 3 months during long-term follow-up. Any clinically significant physical examination findings (abnormalities) observed during the study will be reported as AEs;
  - Vital signs measured at screening (prior to infusion, at the end of infusion, 30 minutes after infusion, 60 minutes after infusion (replaced by 90 minutes after infusion from protocol V7.0) and 4 hours after infusion), at Day 1 (prior to infusion, at the end of infusion, 30 minutes after infusion, 60 minutes after infusion (replaced by 90 minutes after infusion from protocol V7.0) and 4 hours after infusion), Day 2, Day 3, Day 8, Day 15, Day 22 and Day 29 of both cycles 1 and 2, at EOCT/ED visit, at Day 1 (prior to infusion, at the end of infusion, 30 minutes after infusion, 60 minutes after infusion (replaced by 90 minutes after infusion from protocol V7.0) and 4 hours after infusion), Day 2, Day 3, Day 8, Day 15, Day 22 and Day 29 of each additional cycle (if applicable), at EOAC/ED visit (if applicable) and every 3 months during long-term follow-up including supine systolic and diastolic blood pressures, supine heart rate and body temperature;
  - Body weight measured at screening, at Day 1 pre-dose (and up to 24 (replaced by up to 48 hours from protocol V7.0) hours before IMP infusion for cycle 1 only), Day 15 and Day 29 of both cycles 1 and 2, at EOCT/ED visit, at Day 1, Day 15 and Day 29 of each additional cycle (if applicable), at EOAC/ED visit (if applicable) and every 3 months during long-term follow-up;

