A TEAE for the long-term follow-up period is defined as any AE that occurs during the long-term follow-up period of the study if:

- It was not present prior to EOCT/ED visit or EOAC/ED visit, or
- It was present prior to EOCT/ED visit or EOAC/ED visit but the grade increased between EOCT/ED visit or EOAC/ED visit and end of study,
- It was present prior to EOCT/ED visit or EOAC/ED visit, the grade is the same but the causality changed to “related” between EOCT/ED visit or EOAC/ED visit and end of study.

In addition, adverse events will be assigned to a specific cycle of treatment for core trial and additional cycles. This assignment will be based on the start date of the adverse event: if the AE start date is on or after the date of treatment X and before the date of treatment X+1 (or if the subject does not receive a treatment X+1 or the treatment X+1 date is missing), then the TEAE will be assigned to Treatment Cycle X.

An overall summary table of all AEs will be presented by treatment group and overall, by cycle (if applicable) and overall, after IMP screening administration, for core trial, additional cycles and follow-up long term separately. In addition, an overall summary table will be presented by pooling cycles from core trial and additional cycles.

TEAEs will be summarised by treatment group and overall with the number and percentage of subjects with AEs classified by primary system organ class and preferred term, by cycle (if applicable) and overall, after IMP screening administration, for core trial, additional cycles and follow-up long term separately. The number of occurrences of a TEAE will also be presented.

In addition, summary tables will also be presented for related TEAEs, SAEs, related SAEs, non-serious TEAEs, TEAEs by decreasing frequency, TEAEs by NCI-CTCAE worst grade (for NCI-CTCAE worst grade  $\geq 3$ ) and TEAEs by most serious causality (category related only).

Summary of TEAEs and related TEAEs will be also summarised by pooling cycles from core trial and additional cycles.

DLTs during cycle 1 or 2 (i.e. occurring between the first administration of Lu-3BP-227 and EOCT/ED) will be summarised by treatment group and overall with the number and percentage of subjects with DLTs classified by primary system organ class and preferred term. The number of occurrences of a DLT will also be presented.

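### The follow-up TEAE tables mix two collection rules: all-cause adverse events are collected for at most 6 months and only related ones after that, so the all-cause figures are too low

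*SAP*

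**What the plan says.** Protocol 6.2.3 sets the first part of the collection rule: "All AEs and serious adverse events (SAEs) are to be reported up to 6 months after the EOCT, ED or EOAC visit", cut short by new antitumour treatment. Protocol 8.1.2.3 words the cut-off as "or until new antitumour treatment starts, whichever comes first". For the rest of follow-up, 6.2.3 states: "Thereafter, only AEs and SAEs related to the IMP or study procedure should be reported for the remainder of the safety follow-up period". Protocol 8.1.1 and footnote z of Protocol Table 8 give the same rule. The SAP repeats it in 1.3.2.1 ("AEs reported after this timepoint up to the end of the 5-year follow-up should only be reported if evaluated as related") and in footnote z of its Table 1. Follow-up lasts up to 5 years.

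SAP 3.2.1.1 then defines the follow-up TEAE without reference to that rule: "A TEAE for the long-term follow-up period is defined as any AE that occurs during the long-term follow-up period of the study". Its only upper limit is the end of the study. Long-term follow-up is one reporting period, with number and percentage of subjects and number of occurrences by system organ class and preferred term. Further tables cover related TEAEs, SAEs, related SAEs and non-serious TEAEs. SAP 3.2.22 takes all subjects in the population as the denominator. Neither document splits follow-up at 6 months or at new therapy, plans exposure-adjusted rates, or asks for a footnote.

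On fatal events, Protocol 8.1.7 says: "All AEs resulting in death during the study period must be reported as SAEs".

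**The concern.** A table headed as all TEAEs in follow-up would be read as all-cause incidence over that follow-up. It would in fact be all-cause for the first part and related-only for the rest, with nothing on the page to mark the change. Unrelated events after the window are absent because nobody was asked to report them. The SAE and non-serious tables have the same gap.

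The related-event tables sit alongside and are complete over the whole period. A reader who sets one against the other will conclude that a larger fraction of late events is due to the drug than is true. The amendment rationale ties the longer follow-up to late risks such as secondary malignancy, so these tables should say plainly what they count.

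**Working it through.** **Direction.** Let R be the related events in follow-up, U1 the unrelated events inside the full-collection window, and U2 the unrelated events after it.

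- True all-cause count: R + U1 + U2. Recorded: R + U1. The shortfall is U2, which is never negative.
- True related fraction: R/(R + U1 + U2). Recorded: R/(R + U1). The recorded value is larger whenever R and U2 are both above zero.
- Subjects with at least one related event: unchanged, because R is collected throughout.

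None of this needs a numerical assumption.

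**Window length.** Full collection covers at most 6 of 60 months, or 10% of the maximum follow-up, and less once new therapy starts.

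**Size.** The documents give no adverse-event rates, related fraction or survival for follow-up, so there is no planned figure to reproduce. As an illustration, assume 0.10 unrelated and 0.02 related events per subject-month at constant rates (true related fraction 0.02/0.12 = 16.7%), and exponential survival from the start of follow-up, capped at 60 months.

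Hand check at median survival of 4 months:

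- Mean follow-up is 4/ln 2 = 5.77 months.
- Mean time inside the window is 5.77 × (1 − 2^(−6/4)) = 3.73 months.
- Recorded related fraction is 0.02 × 5.77 / (0.02 × 5.77 + 0.10 × 3.73) = 0.115/0.488 = 23.6%.

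Simulation of 1,000,000 subjects per scenario gives the table below. A is the 6-month limit alone. B adds new therapy at an assumed median of 3 months.

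| Median survival (months) | Any TEAE, true | Any TEAE, recorded A | Any TEAE, recorded B | Related fraction of events, A | Related fraction of events, B |
|---|---|---|---|---|---|
| 4 | 40.9% | 35.6% | 26.7% | 23.6% | 33.9% |
| 6 | 51.0% | 42.2% | 31.9% | 28.6% | 40.7% |
| 12 | 67.5% | 53.0% | 42.1% | 39.8% | 54.1% |
| 24 | 80.6% | 63.2% | 53.3% | 50.9% | 65.2% |

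The shortfall in subjects with any TEAE runs from 40.9 − 35.6 = 5.3 to 80.6 − 63.2 = 17.4 points under A, and from 14.2 to 27.3 points under B. Two other rate pairs (0.20 and 0.02; 0.05 and 0.01) widen these ranges to about 4 to 26 points under A and 11 to 34 points under B.

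**Check on the fix.** If the all-cause table stops at the end of the window, both event types are counted over the same time and the related fraction returns to 16.7%. If every subject's follow-up ends within 6 months and no new therapy starts, recorded and true values coincide.

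**The case against.** The strongest reply is that the harm is limited. The DLT period ends at the end-of-core-trial or early-discontinuation visit, so the primary endpoint is untouched. Core-trial and additional-cycle events are tabulated apart from follow-up, and the pooled TEAE tables combine only those two periods. Follow-up data go into a report addendum, listings carry start dates, and the SAP itself states the collection rule. Entry requires estimated life expectancy of only more than 3 months, so many subjects may never leave the window. All of this stands and keeps the point modest. It does not correct the tables. Early new therapy works the other way, because it closes the window sooner.

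Four stronger readings are tempting, and the documents do not support them.

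- A reader might infer that the related-event percentages are inflated. They are not: related events are collected throughout, and the SAP plans no related-to-all ratio. The distortion arises only when the two sets of tables are compared.
- A reader might calculate with fixed follow-up that a true related fraction of 10% shows as 0.10 × 60 / (0.10 × 60 + 0.90 × 6) = 53% at 5 years. That needs every subject to be alive and observed for 60 months, which is not credible in this population.
- A reader might infer that cohort comparisons confound dose with follow-up length, because the amendment extended follow-up from 2 to 5 years. That is possible but not shown. The current text gives everyone a maximum of 5 years, nothing says earlier cohorts were held to 2, and no formal safety comparison is planned.
- A reader might infer that Protocol 8.1.7 flatly contradicts 8.1.1 and that deaths are lost. Protocol 8.1.1 speaks of the study period and then, separately, of the 6 months after treatment, so 8.1.7 may mean the shorter span. Protocol 8.1.2.3, however, places end of study for adverse-event reporting at the end of the 5-year follow-up or death, and on that reading 8.1.7 reaches late unrelated deaths as well. This is an ambiguity of terms. Deaths are still captured through survival status, the death listing and overall survival.

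**Conclusion.** The concern holds for the all-cause follow-up tables. SAP 3.2.1.1 counts any adverse event over a period in which, after at most 6 months, "AEs/SAEs should only be reported if the event is evaluated as related to the IMP or study procedure by the investigator". The direction is certain: for subjects followed past the window, all-cause counts and percentages can only be too low, and the comparison with related events can only overstate how often events are related.

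The size cannot be derived from the documents. The figures above rest on assumed constant event rates, exponential survival and an assumed time to new therapy. They range from no effect, when follow-up ends inside the window, to a substantial shortfall with long survival or early new therapy.

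Restricting collection is a legitimate protocol choice. The fault is that the tables do not follow it. Protocol 12.2.5 defines TEAEs for the active phase only, so the follow-up TEAE is the SAP's own addition, and the SAP can define it to match what is collected. This is an inexpensive improvement to reporting. It does not threaten the trial's primary conclusions.

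**What to change.** In SAP 3.2.1.1, divide long-term follow-up at the end of full collection, that is at 6 months after the relevant visit or at new antitumour treatment if earlier.

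- Restrict the all-cause TEAE, SAE and non-serious follow-up tables to the first window.
- After it, tabulate related adverse events and SAEs only.
- Give no all-cause percentage across both windows.
- Footnote the collection rule on every follow-up table.
- Report the number of subjects and the length of follow-up in each window.

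Rates per subject-month are optional. With three to five subjects per cohort they would be unstable.

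Separately, reconcile Protocol 8.1.7 with 8.1.1 and 8.1.2.3, so that sites know which deaths after the window are to be reported as SAEs.

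The cost is SAP wording and one extra split of existing tables. Event start dates and subsequent antitumour treatment are already recorded, so no new data are needed. The protocol clarification is wording only.

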8.2.6.1 Blood Analyses

Venous blood samples will be taken at the timepoints described in the schedule of assessment (Attachment 1, Section 19.1). Samples collected at Day 1 are to be taken predose, samples collected at Day 2 are to be collected at 24 hours ± 2 hours.

An estimation of the amount of blood required is provided in Attachment 2, Section 19.2.

The parameters to be assessed are listed in Attachment 3, Section 19.3.

For the determination of renal function, eGFR will be calculated by using the MDRD formula preferably; other methods to estimate renal function are acceptable if they are validated measures such as creatinine clearance by Cockcroft & Gault. Hormone analyses will only be performed for subjects who do not have substitution or therapy impacting one of the respective pituitary axis (e.g. no cortisol sampling in subjects who receive corticosteroids, no thyroid-stimulating hormone and free thyroxine sampling in subjects who have thyroxine substitution.

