- a the ED visit will take place within 14 days after ED from the study and at the latest 5 weeks after the last IMP administration, the visit will correspond to an EOCT visit. For subjects who received the screening IMP administration and found ineligible to participate to the study, an ED visit will be performed within 5 weeks (+ 2 weeks) after the IMP screening administration to assess the safety. At least, clinical laboratory tests (e.g. haematology and biochemistry), AEs and concomitant medication/therapy will be collected. If the subject is not able to come for an on-site visit, the visit may be performed by phone call. The clinical laboratory tests may be done locally.
- b follow-up visits will take place every 3 months (±2 weeks) and will start after the EOCT, ED or EOAC visit. Efficacy will be assessed until disease progression, administration of any other chemotherapy or radiotherapy, lost to follow-up, withdrawal of consent, death or a maximum of 2 years, whichever occurs first (see Section 6.2.3). After disease progression is confirmed, no further CT/MRI scans will be required for tumour/disease assessment. The survival status and safety of the subjects will continue to be monitored as indicated in Section 8.1.2.3 until lost to follow-up, withdrawal of consent, death or a maximum of 5 years, whichever occurs first.
- c the screening period can be extended by two weeks if this is required for logistical reasons.
- d Day 1 of Cycle 1 is the day of the first treatment administration. Day 1 of Cycle 2 and each potential subsequent cycle may coincide with Day 29 of the previous cycle if all safety assessments are performed and allow for the next administration.
- e in case of toxicity requiring a delay, the next treatment administration will be delayed by up to 4 weeks.
- f whole body ceCT or ceMRI including brain unless a similar exam has already been performed within 1 month prior to Day -21.
- g Cycle 1 Day 1 ¹⁸FDG-PET between Day -21 and Day 1.
- h screening administration will be done after confirmation of eligibility (i.e. after all other screening assessments have been performed), minimum 1 week before the first treatment administration.

Procedures and			CORE TRIAL [v]										EOCT	Long-term							
assessments	Screening		Treatment Period								or	Follow-up									
	Screening				Cycle 1					Cycle 2									ED [a]	[b]	
	D-21 to D-1	D1 [d]	D2	D3	D4	D5	D7	D 15	D 22	D29	D1 [d]	D2	D3	D4	D5	D7	D15	D22	D29	D43	

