#### **3.2.1.1 Adverse events**

AEs will be coded using the Medical Dictionary for Regulatory Activities (MedDRA) latest version at Ipsen coding department at the time of corresponding database lock and NCI-CTCAE version 5.0 will be used for the grade's classification.

Listings will be presented by treatment group, subject, start date-time, primary system organ class, preferred term and reported term for all AEs recorded during the study, after IMP screening administration, for core trial, additional cycles and follow-up long term separately.

Listings of all AEs, serious adverse events (SAE), AEs leading to withdrawal and listing of deaths will also be presented.

TEAEs will be flagged (\*) in the listing of AEs and will be summarised.

A TEAE for the IMP screening administration is defined as any AE that occurs after the IMP screening administration if:

- It was not present prior to IMP screening administration and it had onset before the first dose of IMP during core trial, or
- It was present prior to receiving the IMP screening administration but the grade increased between IMP screening administration and the first dose of IMP during core trial,
- It was present prior to receiving the IMP screening administration, the grade is the same but the causality changed to "related" between IMP screening administration and the first dose of IMP during core trial.

A TEAE for the core trial period is defined as any AE that occurs during the core trial period of the study if:

- It was not present prior to first dose of IMP during core trial period and it had onset before the EOCT/ED visit, or
- It was present prior to receiving the first dose of IMP during core trial period but the grade increased between first dose of IMP during core trial period and EOCT/ED visit,
- It was present prior to receiving the first dose of IMP during core trial period, the grade is the same but the causality changed to “related” between first dose of IMP during core trial period and EOCT/ED visit.

A TEAE for the additional cycles period is defined as any AE that occurs during the additional cycles period of the study if:

- It was not present prior to EOCT visit and it had onset before the EOAC/ED visit, or
- It was present prior to EOCT visit but the grade increased between EOCT visit and EOAC/ED visit,
- It was present prior to EOCT visit, the grade is the same but the causality changed to “related” between EOCT visit and EOAC/ED visit.

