The number of subjects with at least one DLT or NCI-CTCAE grade  $\geq 2$  (excluding hair loss) will be tabulated by treatment group and overall, by cycle and overall.

Listings of all DLTs will also be presented.

Depending on the number of cases, for all SAEs linked to COVID-19, a summary table will also be provided by treatment group and overall, presenting the number of patients by SOC and PT, by pooling core trial, additional cycles and follow-up long term. Listings of all SAEs linked to COVID-19 will also be presented.

In the event of multiple reports of the same preferred term being reported by the same subject, the NCI-CTCAE worst grade (grade 5 > grade 4 > grade 3 > grade 2 > grade 1) and the most serious causality (related > not related) will be chosen.

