If the start date of the adverse event is identical to the date of last administration, then “<1” day will be presented with the duration in hh:mm recorded in the eCRF if it is available. Otherwise, it will be calculated as (start date/time - last administration date/time) and presented in days days hh:mm. If at least one time is missing and if the duration is greater than 24 hours then it will be calculated as (start date – last administration date) + 1 and presented in days. If the start date and the associated information do not allow to state about the last dose received (partial start date or start at administration day without knowing if it started before or after the drug intake), all the possible time since last dose will be presented [i.e.: if a subject received a daily administration and reported an AE at second administration day but without indication about before or after the drug intake the time since last dose will be as “2 / <1”]. If the start date is partial, the time since last dose will be presented as an superior inequality (i.e.: for an AE started in FEB2004 after the only administration performed on 31JAN2004, the time since last dose will be as “≥2” days). If the start date is missing the time since last dose will not be presented although the AE will be assigned to each dose received before its end date.

CCI

CCI

CCI

CCI

CCI

CCI

CCI

CCI

CCI

CCI

CCI

CCI

CCI

CCI

CCI

CCI

CCI

CCI

[figure not shown]

CCI

CCI

CCI

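### The SAP assigns TEAEs to cycles by start date alone, which does not match its own TEAE definition, so some events will be missing from or misplaced in the by-cycle TEAE and DLT/Grade ≥2 tables

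*SAP*

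**What the plan says.** SAP Section 3.2.1.1 gives three routes to a core-trial TEAE. One is new onset. The second is a worsening: "It was present prior to receiving the first dose of IMP during core trial period but the grade increased". The third is an event already present at the same grade whose causality changes to related. The additional-cycles period has the same three routes; its worsening route reads "It was present prior to EOCT visit but the grade increased between EOCT visit and EOAC/ED visit".

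The section then assigns events to cycles. "This assignment will be based on the start date of the adverse event", and the event belongs to Cycle X "if the AE start date is on or after the date of treatment X and before the date of treatment X+1", or if no further treatment was given. No other date enters the rule.

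The assignment feeds the AE overview and the TEAE tables by SOC and PT, which are split by cycle where applicable. It also feeds the count of subjects with a DLT or a Grade ≥2 event, which "will be tabulated by treatment group and overall, by cycle and overall". Protocol Section 12.2.4 plans that last table too, by radioactivity level and cycle.

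On timing, Protocol Section 8.2.6.1 states "Samples collected at Day 1 are to be taken predose". Footnote d of Table 8 (Protocol Attachment 1) says that Day 1 of Cycle 2 "may coincide with Day 29 of the previous cycle".

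**The concern.** Two of the three routes concern events that start before the period in question. A rule that reads only the start date cannot place them in the cycle in which they qualified. A core-trial TEAE of this kind starts before treatment 1 and so meets the condition for no cycle. An additional-cycles TEAE of this kind starts before EOCT and goes to a core cycle or to none.

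Such records will exist. Protocol Section 8.1 collects AEs from consent. Protocol Section 6.2.1 places the screening administration at least one week before Day 1, and the SAP defines TEAEs for that administration as well.

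The cycle matters because Protocol Section 4.2.1.1 defines the MTSA by DLTs in Cycle 1 and the MTCA by DLTs in Cycles 1 and/or 2. The DLT/Grade ≥2 table is the only planned summary that splits DLTs by cycle, and cohorts are small enough for one misplaced event to change its reading.

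**Working it through.** The plan states no figure on this point, so the check applies the rule to test records.

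**Assumed study days.** Cycle 1 dose on day 1; Cycle 2 dose on day 29; EOCT on day 71 (29 + 42, six weeks after dose 2); first and second additional doses on days 78 and 106; EOAC on day 148 (106 + 42).

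**Rule.** Cycle X if date of treatment X ≤ AE start date < date of treatment X+1.

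**Results when one record keeps its original start date:**

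| Record | TEAE route | Cycle by SAP rule | Cycle in which it qualified or arose |
|---|---|---|---|
| Starts day −5, grade rises day 15 | Core, worsening | None (−5 < 1) | Cycle 1 |
| Starts day −5, grade rises day 40 | Core, worsening | None (−5 < 1) | Cycle 2 |
| Starts day −5, same grade, becomes related day 15 | Core, causality | None (−5 < 1) | Cycle 1 |
| Starts day 20, reaches DLT grade day 45 | Core, onset | Cycle 1 (1 ≤ 20 < 29) | Cycle 2, as a DLT |
| Starts day 40, grade rises day 90 | Core, onset; additional cycles, worsening | Cycle 2 (29 ≤ 40 < 78) | Additional cycle 1, for the worsening |
| Laboratory AE dated to the predose sample on day 29, dose 2 given | Core, onset | Cycle 2 (29 ≤ 29 < 78) | Cycle 1 |

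**Results when each grade increase opens a new record.** The four grade-increase rows move to the right-hand column and the rule works for them. The causality row does not move: the grade is unchanged, so nothing has deteriorated that would generate a record with a later start date. The predose row does not move either, because the fault there is the date-only boundary.

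**Effect on a Cycle 1 proportion.** Cohort size is 3 to 5 (Protocol Section 4.2.1.2). Take a cohort with no other Cycle 1 DLT and one DLT that arose in Cycle 2 but is booked to Cycle 1. The tabulated Cycle 1 DLT proportion goes from 0/n to 1/n:

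- n = 3: 0% to 33.3%
- n = 4: 0% to 25.0%
- n = 5: 0% to 20.0%

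**Exposure to the same-day boundary.** In Table 8 the haematology and biochemistry draws after dose 1 and before dose 2 are Days 7, 15, 22 and 29 and the predose Cycle 2 Day 1 draw. One of five (20%) carries the date of treatment 2, or one of four (25%) if Day 29 and Cycle 2 Day 1 coincide. These are shares of scheduled draws, not of events.

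**The case against.** The strongest reply is that the grade-increase cases depend on a recording convention that neither document states. Protocol Section 8.1.1 counts deterioration of an existing condition as an AE. Protocol Section 8.2.6 makes a laboratory abnormality reportable when it suggests toxicity that is new or worse than baseline. SAP Section 3.2.1.1 anticipates several reports of one preferred term in one subject. A condition present at entry may sit in medical history or baseline signs and symptoms (SAP Sections 3.2.6 and 3.2.7), with its later worsening entered as a fresh AE. If that is the practice, the rule places worsened events correctly.

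This stands as a condition, but it does not dispose of the point. It cannot help the causality route. If every increase were a new record, the onset route would already capture it and the worsening route would be largely redundant, so the definition reads as though written for one evolving record. Protocol Section 8.1.2.2 has continuing AEs reviewed at each assessment and does not call for a new record.

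Several limits also stand:

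- The DLT summary by SOC and PT runs from first administration to EOCT/ED without a cycle split, and all DLTs are listed.
- Laboratory worst grades by cycle come from the laboratory values (SAP Section 3.2.1.2).
- A DLT recognised on the predose Cycle 2 sample stops further treatment (Protocol Section 4.7.1). There is then no next treatment and the event stays in Cycle 1.
- Where that stopping rule is followed, a DLT in a subject who received dose 2 arose after dose 2, so its cycle can be recovered from the DLT and dosing listings.
- The TEAE table by worst grade is not said to be split by cycle.

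SAP Appendix 1 says of an AE with a missing start date "although the AE will be assigned to each dose received before its end date". A reader might infer that such events are counted repeatedly in the cycle tables. That sentence defines time since last dose, and SAP Section 3.2.2.2 has a separate rule for missing dates, so the inference is not supported.

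**Conclusion.** The cycle rule and the TEAE definition in SAP Section 3.2.1.1 do not fit together. Causality-change TEAEs will be unassigned or misplaced. Grade-increase TEAEs will be too, unless each increase is entered as a new record. Non-dose-limiting AEs dated to the predose Cycle 2 Day 1 sample will be credited to Cycle 2. The tables affected are the by-cycle AE and TEAE tables and the by-cycle DLT/Grade ≥2 table.

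The 20–33% shift in a cohort's Cycle 1 DLT proportion is an illustration. It assumes one event on a single record and no other Cycle 1 DLT in that cohort. The documents do not say how many TEAEs will qualify by worsening or causality, so no overall share can be given.

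Two stronger readings are tempting and not supported. One is that all by-cycle toxicity tables are wrong or that DLTs are lost; the overall counts, the DLT summary, the DLT listing and the laboratory grades do not use the rule. The other is that MTSA or MTCA decisions will be wrong. The SRC decides on all available data, with optional modelling (Protocol Section 12.2.8), and no section bases those decisions on this table. The harm is to the reported picture of toxicity by cycle.

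**What to change.** In SAP Section 3.2.1.1, assign each TEAE to the cycle in which its TEAE criterion was met, using the date of onset, grade increase or causality change as applicable. In the DLT/Grade ≥2 table, assign a DLT by the date on which the DLT criterion was met. Use date and time, or a predose flag, so that an event before the infusion on the day of treatment X+1 belongs to Cycle X. State whether a grade increase opens a new AE record.

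The cost is SAP wording and some programming. Where one record holds several grades or causality assessments, the change dates must be available from the eCRF or, for laboratory events, from the laboratory data.
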